10.3. Quality Control (Study Monitoring)

In accordance with applicable regulations including GCP, and GSK procedures, GSK or designee (i.e. third party vendor) monitors will contact the site prior to the start of the study to review with the site staff the protocol, study requirements, and their responsibilities to satisfy regulatory, ethical, and GSK requirements.

When reviewing data collection procedures, the discussion will include identification, agreement and documentation of data items for which the CRF will serve as the source document.

GSK or designee will monitor the study and site activity to verify that the:

1. Data are authentic, accurate, and complete.
2. Safety and rights of subjects are being protected.
3. Study is conducted in accordance with the currently approved protocol and any other study agreements, GCP, and all applicable regulatory requirements.

The extent and nature of monitoring will be described in a written monitoring plan on file at GSKCH. The investigator (or designee) agrees to allow the monitor direct access to all relevant documents and agrees to co-operate with the monitor to ensure that any problems detected in the course of these monitoring visits are resolved.

10.4. Quality Assurance

To ensure compliance with GCP and all applicable regulatory requirements, GSK may conduct a quality assurance assessment and/or audit of the site records, and the regulatory agencies may conduct a regulatory inspection at any time during or after completion of the study.

In the event of an assessment, audit or inspection, the investigator (and institution) must agree to grant the advisor(s), auditor(s) and inspector(s) direct access to all relevant documents and to allocate their time and the time of their staff to discuss the conduct of the study, any findings/relevant issues and to implement any corrective and/or preventative actions to address any findings/issues identified.

 GlaxoSmithKline	Document Name	Clinical Protocol 207782		
	Type	Version	Document Identifier	Effective Date
	eldo_clinical_doc	2.0; Most-Recent; Effective; CURRENT	090032d580d48db0	26-May-2017 05:53:15
	Reason For Issue	Auto Issue		

The sponsor will be available to help investigators prepare for an inspection.

10.5. Conditions for Terminating the Study

Upon completion or premature discontinuation of the study, the GSKCH monitor will conduct site closure activities with the investigator or site staff, as appropriate, in accordance with applicable regulations including GCP, and GSKCH Standard Operating Procedures.

Both GSKCH and the Investigator reserve the right to temporarily suspend or prematurely discontinue this study at any time for reasons including, but not limited to, safety or ethical issues or severe non-compliance. For multicenter studies (if applicable), this can occur at one or more or at all sites.

If the trial is prematurely terminated or suspended for any reason, the investigator site should promptly inform the trial subjects and should assure appropriate therapy/ follow-up for the subjects. Where required by the applicable regulatory requirements, GSKCH should inform the regulatory authority(ies).

In addition:

1. If the investigator terminates or suspends a trial without prior agreement of GSKCH, the investigator site should promptly inform the sponsor and the IRB, and should provide the sponsor and the IRB a detailed written explanation of the termination or suspension.
2. If the GSKCH terminates or suspends a trial, the investigator should promptly inform the IRB and provide the IRB a detailed written explanation of the termination or suspension.
3. If the IRB terminates or suspends its approval/favorable opinion of a trial, the investigator should promptly notify the GSKCH and provide GSKCH with a detailed written explanation of the termination or suspension.

10.6. Records Retention

Following closure of the study, the investigator must maintain all site study records (except for those required by local regulations to be maintained elsewhere), in a safe and secure location.

The records (study/ site master file) must be maintained to allow easy and timely retrieval, when needed (e.g., for a GSK audit or regulatory inspection) and must be available for review in conjunction with assessment of the facility, supporting systems, and relevant site staff.

 GlaxoSmithKline	Document Name	Clinical Protocol 207782		
	Type	Version	Document Identifier	Effective Date
	eldo_clinical_doc	2.0; Most-Recent; Effective; CURRENT	090032d580d48db0	26-May-2017 05:53:15
	Reason For Issue	Auto Issue		

Where permitted by local laws/regulations or institutional policy, some or all of these records can be maintained in a format other than hard copy (e.g., microfiche, scanned, electronic); however, caution needs to be exercised before such action is taken.

The investigator must ensure that all reproductions are legible and are a true and accurate copy of the original and meet accessibility and retrieval standards, including re-generating a hard copy, if required. Furthermore, the investigator must ensure there is an acceptable back-up of these reproductions and that an acceptable quality control process exists for making these reproductions.

The investigator must assure that the subject's anonymity will be maintained. On CRFs or other documents submitted to GSKCH, subjects should not be identified by their names or initials, but by an identification code. The investigator should keep a separate log of subjects' codes, names and addresses. Documents not for submission to GSKCH, e.g. subjects' written consent forms, should be maintained by the investigator in strict confidence.

GSK will inform the investigator of the time period for retaining these records to comply with all applicable regulatory requirements (GSKCH recommends that documents be kept for 10 years). The investigator is also required to keep subject identification codes on file for at least 20 years after completion or discontinuation of the study. The minimum retention time will meet the strictest standard applicable to that site for the study, as dictated by any institutional requirements or local laws or regulations, GSK standards/procedures, and/or institutional requirements.

No study document should be destroyed without a prior written agreement between GSKCH and the investigator. The investigator must notify GSK of any changes in the archival arrangements, including, but not limited to, archival at an off-site facility or transfer of ownership of the records in the event the investigator is no longer associated with the site.

10.7. Provision of Study Results to Investigators, Posting of Information on Publicly Available Clinical Trials Registers and Publication

Where required by applicable regulatory requirements, an investigator signatory will be identified for the approval of the clinical study report. The investigator will be provided reasonable access to statistical tables, figures, and relevant reports and will have the opportunity to review the complete study results at a GSK site or other mutually-agreeable location.

 GlaxoSmithKline	Document Name	Clinical Protocol 207782		
	Type	Version	Document Identifier	Effective Date
	eldo_clinical_doc	2.0; Most-Recent; Effective; CURRENT	090032d580d48db0	26-May-2017 05:53:15
	Reason For Issue	Auto Issue		

GSK will also provide the investigator with the full summary of the study results. The investigator is encouraged to share the summary results with the study subjects, as appropriate.

The procedures and timing for public disclosure of the results summary and for development of a manuscript for publication will be in accordance with GSK Policy.

A manuscript will be progressed for publication in the scientific literature if the results provide important scientific or medical knowledge.

 GlaxoSmithKline	Document Name	Clinical Protocol 207782		
	Type	Version	Document Identifier	Effective Date
	eldo_clinical_doc	2.0; Most-Recent; Effective; CURRENT	090032d580d48db0	26-May-2017 05:53:15
	Reason For Issue	Auto Issue		

## Document History

Document	Version Date	Summary of Changes (New analysis or Change in planned analysis)
Amendment 1	14-Aug-2017	Added new mandatory listings and incorporated in new template.
Original Analysis Plan	30-Jun-2017	Not applicable (N/A)

Amendments incorporate all revisions to date.

## 1 Summary of Key Protocol Information

The objective of this clinical study is to assess the cutaneous and ocular local tolerance of two cosmetic facial cleansers in healthy females with sensitive skin under normal conditions of use.

### 1.1 Study Design

#### Overall Design

This is an assessor blind (dermatologist and ophthalmologist) clinical in use study to determine the local cutaneous and ocular tolerance of two cosmetic facial cleanser products when used as per the intended instructions for use in a population of healthy female subjects with clinically assessed sensitive skin.

Subjects who have sensitive skin as classified by a positive reaction to a lactic acid Stinging Test will be asked to use one of two cleansing products as part of their normal skin care routine for 3 weeks.

Both test products are the same formulation but are differentiated by the dispensing pack; to either a micellar cleanser or a foaming cleanser.

Subjects will be instructed to cleanse their face with one of the two test products at home twice-daily, for 21 (+ 2) days, including a supervised first application at the study site (Visit 2) and a final application at home on the morning of the final visit (Visit 3), as per the intended instructions for use.

A qualified dermatologist and a qualified ophthalmologist will assess the baseline cutaneous and ocular irritation of prospective subjects at Visit 2. For a subject to be considered eligible to participate in the study, all dermatologist and ophthalmologist assessment scores must be zero. Further dermatologist and ophthalmologist assessments will be completed 1-hour ( $\pm$  20 minutes) post supervised first product use and at the final visit (Visit 3) at the end of the 21 (+2) day product use period. The intensity of any visual signs of cutaneous and ocular irritation will be recorded by the dermatologist and ophthalmologist, according to the assessment scales detailed in section 2.4.1.

The dermatologist will also determine each subject's facial skin type as dry, oily or normal/combination skin. Any subject classified as having oily skin will not be considered eligible for participation in the study as they do not represent the target population for the product.

Subjects will be asked to complete self-assessment questions at Visit 2 prior to any study product use (section 2.4.2). In addition, randomized subjects will be asked to complete the self-assessment questions 1 hour ( $\pm$  20 minutes) post supervised first product use and at the end of the 21 (+2) day product use period.

The objective of this clinical study is to assess the cutaneous and ocular local tolerance of two cosmetic facial cleansers in healthy females with sensitive skin under normal conditions of use.

### Visit 1 – Screening Visit

The following assessments will be conducted:

1. Subject Informed Consent taken
2. Subject demographics collected
3. Medical history details collected
4. Details of current and concomitant medication collected
5. Inclusion/Exclusion criteria
6. Contact lens wearer status assessment (Yes or No)
7. Clinical diagnosis of sensitive skin confirmed by Lactic Acid sting test
8. Determination of subject eligibility to participate in the study
9. Adverse events will be reported following the Lactic Acid stinging test procedure

### Visit 2 – Baseline Visit

#### *Within 7 days of the Screening Visit*

The following assessments will be conducted:

1. Current/Concomitant medications review
2. **INCLUSION/EXCLUSION CRITERIA**
3. Fitzpatrick skin type assessment
4. Dermatologist assessment of skin type status (dry, oily or normal/combination) Inclusion criteria 5e and Exclusion criteria 7f
5. Clinical dermatologist assessment for eligibility to participate in the study (including visual examinations). Inclusion criteria 5c  
**Note:** subject must have a total score of zero for inclusion into the study
6. Clinical ophthalmologist assessment for eligibility to participate in the study (including visual examinations). Inclusion criteria 5d  
**Note:** subject must have a total score of zero for inclusion into the study.
7. Subject self-assessment questions. Prior to product use.
8. Continued eligibility check
9. Randomization and stratification
10. Dispense assigned study product and diary card/instructions for use
11. Supervised first use of assigned product
12. Dermatologist (Appendix 3) and ophthalmologist assessments 1 hour ( $\pm 20$  minutes) post supervised first product application
13. Subject self-assessment questions 1 hour ( $\pm 20$  minutes) post first supervised

use 14. Adverse events assessment
Visit 3 - Week 3 / Exit from Study (21 (+ 2) Days)

The following assessments will be conducted:
 
 
1. Current/Concomitant medications review
 
2. Continued eligibility check
 
3. Return study product and diary card/instructions for use
 
4. Diary card check to confirm compliant product use
 
5. Dermatologist final assessment of tolerance (Appendix 3)
 
6. Ophthalmologist final assessment of tolerance (Appendix 4)
 
7. Subject final self-assessment questions (Appendix 5)
 
8. Adverse event assessment
 
9. Subject discharge from the study site following completion of all study procedures
 

## 1.2 Study Objectives

Objectives	Endpoints
Primary Objective	Primary Endpoint

 
• Assessment of the cutaneous and ocular tolerance of two cosmetic facial cleansers after 21 (+ 2) days of product use per the intended instructions in healthy female subjects with clinically assessed sensitive skin.
 
	
 
• Dermatologist and ophthalmologist visual assessment of cutaneous and ocular irritation after 21 (+ 2) days of test product use.
 

Secondary Objectives	Secondary Endpoints
Assessment of the cutaneous and ocular tolerance of two cosmetic facial cleansers on Day 1 of product use per the intended instructions in healthy female subjects with clinically assessed sensitive skin.	Dermatologist and ophthalmologist visual assessment of cutaneous and ocular irritation on Day 1 of test product use.

 
• Assessment of the cutaneous and ocular tolerance of two cosmetic facial cleansers after 21 (+ 2) days of product use per the intended instructions in healthy female subjects with clinically assessed sensitive skin.
 
• To evaluate the general safety of two cosmetic facial cleansers.
 
	
 
• Subject self-assessment question responses (redness, dryness, burning, itching and stinging) with regards to product use experience on the face and around the eyes after 21 (+ 2) days of test product use.
 
• Frequency and severity of Adverse Events
 

### 1.3 Treatments

The following treatment products will be supplied by the Clinical Supplies Department, GSKCH:

	Test Product 1	Test Product 2
Product Name	Micellar Cleanser	Micellar Foaming Cleanser
Product Formulation Code (MFC)	CCI	
Product Format	200ml Clear plastic bottle	150ml Plastic pump pack
Application Quantity	To be used as per normal home use application	
Route of Administration	Topical dermal application	
Application Instructions	Use morning and evening. Apply to a cotton pad and wipe over the entire face and closed eyes to gently cleanse. No need to rub or rinse. Cotton pads will be supplied.	Use morning and evening. Massage gently onto wet skin on the face using fingertips, rinse thoroughly and pat skin dry.

### 1.4 Sample Size Calculation

A sufficient number of subjects will be screened (up to 170) to randomize approximately 92 subjects (46 per treatment group) to ensure that at least 40 subjects in each treatment group complete the study (80 subjects in total).

Randomization will be stratified by both contact lens wearer status (yes or no) and skin type (dry or normal/combination). The aim is to ensure balance of strata effects between treatment groups.

The sample size is based on clinical considerations to provide descriptive information on the tolerability and safety of the products, and is consistent with ANVISA guidelines (ANVISA, 2012).

## 2 Planned Analyses

### 2.1 Interim Analysis

No interim analysis is planned.

## **2.2 Final Analyses**

The final planned primary analyses will be performed after the completion of the following sequential steps:

1. All subjects have completed the study as defined in the protocol.
2. All required database cleaning activities have been completed and database has been locked.
3. All criteria for unblinding the randomisation codes have been met and the randomisation codes have been distributed.

## **3 Considerations for data analyses and Data Handling Conventions**

### **3.1 Baseline Definition**

For all endpoints the baseline value will be the latest pre-treatment assessment with a non-missing value.

Unless otherwise stated, if baseline data is missing no derivation will be performed and will be set to missing.

### **3.2 Subgroups/Stratifications**

Subjects are randomised by two strata, contact lens wearer (Yes or No) and cosmetic skin type (dry or normal/combination). Efficacy variables will be analysed accounting for strata.

## **4 Data Analysis**

Data analysis will be performed by inVentiv Health Clinical. The statistical analysis software used will be SAS version 9.4 (Studio).

Prior to database closure a Blind Data Review Meeting (BDRM) will be conducted in which various aspects of the trial will be discussed and agreed.

Except as described below, all listings will be produced for all randomized subjects.

### **4.1 Populations for Analysis**

Tables described in this section other than disposition will be produced for all randomized subjects.

#### **4.1.1 Subject Disposition**

Screen failures will be defined as subjects who do not satisfy all the inclusion/exclusion criteria. A summary will be provided of the number of subjects screened and the number of screen failures with reasons why subjects were not randomized.

Subject disposition will be summarized as the number and percentage of subjects (out of the number of randomised subjects) who complete the study, with the number who discontinue broken down by reason for discontinuation ([Table 14.1.1](#)). The table will also summarize the number and percent of subjects assigned to each analysis population (refer to section 4.1.3).

Subject disposition including the subject status (completer, Yes/No), critical demographic data (age, sex, race), the duration of treatment before discontinuation and the specific reason for discontinuation, will be listed in [Listing 16.2.1.1](#) by treatment group.

#### 4.1.2 Protocol Deviations

Protocol violations will be tracked by the study team throughout the conduct of the study. A per protocol analysis is not planned for this study, but data will be reviewed prior to unblinding and closure of the database.

All-important violations will be defined in the “Review Listing Requirement (RLR)” document.

A list of protocol deviations will be provided in [Listing 16.2.2](#).

#### 4.1.3 Analysis Populations

Two analysis populations are defined.

Population	Definition / Criteria	Analyses Evaluated
Safety	
 
Comprises of all subjects for whom the lactic acid stinging test was performed.
 
This population will be based on the treatment the subject actually received.
 
	
 
Safety
 

Intent-To-Treat	
 
Comprises of all randomized subjects who have at least one cutaneous or ocular assessment following study product application.
 
This population will be based on the treatment the subject is randomised to.
 
	
 
Efficacy
 

**NOTES :**

- Please refer to Attachment 1: List of Data Displays which details the population to be used for each displays being generated.

### 4.2 Subject Demographics and Other Baseline Characteristics

Demographic and baseline characteristics summaries will be produced for the ITT and Safety populations by treatment group.

#### 4.2.1 Demographic Characteristics

These summaries will include age, gender, race and strata. It will also include Fitzpatrick skin type. Categorical measures (gender, race, contact lens wearer status, Fitzpatrick skin type and

cosmetic skin type) will be summarised by the number and percentage of subjects in each category. Descriptive statistics for age will include the mean, median, standard deviation and minimum/maximum.

#### **4.2.2 General Medical History**

Medical history data will not be presented in the study report. A data listing will be produced only at the blinded data review stage.

### **4.3 Treatments (Study Drug/Product, Rescue Medication, other Concomitant Therapies, Compliance)**

#### **4.3.1 Study Product/Drug Compliance and Exposure**

Treatment compliance (number of missed uses and number of additional uses) will be listed for the blinded data review.

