6.3. Visit 3 - Last Subject Last Visit (LSLV) and Study Conclusion

Subjects will return to the study site after 21 (+ 2) days of twice daily product use. Subjects will return their test products and diary card. The diary card will be reviewed to check compliance and evaluate subject comments. The total number of product applications and total number of missed product applications will be recorded in the CRF.

Final dermatologist (per section 6.2.5) and ophthalmologist (per section 6.2.6) assessments will be completed and the subject will answer the self-assessment questions (Appendix 5) based on their experience of using the product.

 GlaxoSmithKline	Document Name	Clinical Protocol 207782		
	Type	Version	Document Identifier	Effective Date
	eldo_clinical_doc	2.0; Most-Recent; Effective; CURRENT	090032d580d48db0	26-May-2017 05:53:15
	Reason For Issue	Auto Issue		

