9.2. General Considerations

9.2.1. Definition of Analysis Populations

The ‘Intent to treat’ (ITT) population includes all subjects who are randomized into the study and have at least one cutaneous or ocular assessment following study product application.

A separate Per Protocol (PP) analysis will not be performed. Protocol deviations will however be listed for review.

The Safety population includes all subjects from the point of the lactic acid stinging test procedure until completion of the study.

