9.2.3. Criteria for Evaluation of Local Tolerance

The primary evaluation will be dermatologist and ophthalmologist visual assessments of local tolerance after 21 (+2) days of twice-daily study product application using the ITT population.

This study will be considered a success if the majority (i.e. >50%) of subjects per treatment arm complete the study with combined dermatologist and ophthalmologist scores of zero at day 21 (+ 2).

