#### **4.4.1.2 Statistical Hypothesis, Model, and Method of Analysis**

No formal statistical inference will be performed.

The combined dermatologist and ophthalmologist score will be summarized using frequencies and percentages by treatment group and time point, with Day 21 results of primary interest. The sum across post-baseline observations for the combined dermatologist and

ophthalmologist score will also be summarized using frequencies and percentages by treatment group.

Similar summaries will also be provided for the following variables:

[figure not shown]
- Combined dermatologist and ophthalmologist score (modified) = dermal response score + conjunctiva involvement score + lacrimal intensity score
- Combined dermatologist score
- Combined ophthalmological score
- Dermal response score
- Conjunctiva involvement score
- Lacrimal intensity score

Data will also be presented by sub-groups (strata), contact lens wearer status (not contact lens wearer, contact lens wearer) and skin type (dry, normal/combination) by the following categories:

- Not contact lens wearer with dry skin
- Contact lens wearer with dry skin
- Not contact lens wearer with normal/combination skin
- Contact lens wearer with normal/combination skin.

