### 4.1 Populations for Analysis

#### 4.1.1 Subject Disposition

Screen failures will be defined as subjects who do not satisfy all the inclusion/exclusion criteria. A summary will be provided of the number of subjects screened and the number of screen failures with reasons why subjects were not randomized. Additionally, the number and percentage of subjects who underwent the lactic acid sting test will also be presented ([Table 14.1.1](#)).

Subject disposition will also be summarized as the number and percentage of subjects (out of the number of randomised subjects) who complete the study, with the number who discontinue broken down by reason for discontinuation ([Table 14.1.1](#)). The table will also summarize the number and percent of subjects assigned to each analysis population (refer to section 4.1.3).

Subject disposition including the subject status (completer, Yes/No), critical demographic data (age, sex, race), the duration of treatment [(date of completion or withdrawal - treatment start date)+1] before discontinuation and the specific reason for discontinuation, will be listed in [Listing 16.2.1.1](#), by treatment group.

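### Product use is recorded but neither summarised by arm nor linked to the Day 21 result, so a woman who stopped the cleanser and returns with clear skin counts as a tolerance success

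*SAP*

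**What the plan says.** The target of the primary evaluation is stated in Protocol 9.2.3: "visual assessments of local tolerance after 21 (+2) days of twice-daily study product application using the ITT population". Twice-daily use is thus part of the question.

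Use is measured. Protocol 5.2 has each application entered on a diary card and gives an expected total of 42 to 46. Protocol 6.3 adds: "The total number of product applications and total number of missed product applications will be recorded in the CRF".

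The analysis does not draw on it:

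- SAP 4.3.1: "Treatment compliance (number of missed uses and number of additional uses) will be listed for the blinded data review". Attachment 1 has no compliance or exposure table or listing.
- Protocol 9.2.1: "A separate Per Protocol (PP) analysis will not be performed". Protocol 9.2.2 excludes no data from any analysis.
- The ITT set (SAP 4.1.3, unchanged in Addendum 1) requires randomisation and one skin or eye examination after product use. It sets no amount of use.
- The success rule (SAP 4.4.1.1) asks for a zero combined score at Day 21 in more than half of each arm. SAP section 5 records that the reference to completing the study was dropped.

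Two other outputs touch on use. Protocol 6.3.1 treats any use other than twice daily as a deviation and sends missed and extra applications to the Deviations Log, and SAP 4.1.2 lists deviations in Listing 16.2.2. Addendum 1, section 4.1.1, defines the duration shown in Listing 16.2.1.1 as "the duration of treatment [(date of completion or withdrawal - treatment start date)+1", so it ends on the completion or withdrawal date and not at last use.

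**The concern.** In a tolerance study, non-use favours the sponsor's conclusion. Every subject must score zero before first use, so a woman who reacts, stops and recovers tends to return to zero. The Schedule of Events has no assessor examination between one hour after first use and Visit 3. Under Protocol 6.2.5, 6.2.6 and 7.1.1, an observed response that can be graded on the skin or eye scale is not an adverse event unless it is unusual. A reaction in the second week that led a woman to stop could therefore be absent from both the Day 21 score and the adverse event tables.

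Disposition does not fill the gap, because it records leaving the study and not stopping the product while staying in it. The duration in Listing 16.2.1.1 would show her as fully treated. At stake is whether a reader of the report can separate tolerance of the product from non-use of it.

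**Working it through.** **Step 1: the plan's own figures.**

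- Expected applications (Protocol 5.2): 2 × 21 = 42 and 2 × 23 = 46. Reproduced.
- Enrolment (SAP 1.4): "92 subjects (46 per treatment group) to ensure that at least 40 subjects in each treatment group complete the study". Implied loss is 1 − 40/46 = 13.0%, and 40/(1 − 0.13) = 45.98, rounded up to 46. Reproduced.
- There is no power calculation to reproduce. SAP 1.4: "The sample size is based on clinical considerations to provide descriptive information". SAP 4.4.1.2: "No formal statistical inference will be performed".

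One inconsistency affects any percent-of-expected figure. Protocol 5.2 also describes a supervised first use, a second use that evening, and a use on the morning of Visit 3. Counted that way, the total is 2 + 19 × 2 + 1 = 41 if Visit 3 falls on study day 21, 2 + 20 × 2 + 1 = 43 if it is 21 days after Visit 2, and 2 + 22 × 2 + 1 = 47 if it is 23 days after. These do not match 42 to 46.

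**Step 2: the duration figure.** Take a woman who uses the product for three full days (6 applications), stops, and attends Visit 3 21 days after Visit 2. Her listed duration is 21 + 1 = 22 days, the same as a full user's. Her actual use is 6/42 = 14.3% of the stated minimum.

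**Step 3: how many women decide a result.** Assume that women who stopped attend Visit 3 and all score zero. The documents give no figure for this. More than 50% needs 21 of 40 or 24 of 46.

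| Assessed | Bare pass | Remove 1 stopper | Remove 2 stoppers |
|---|---|---|---|
| 40 | 21/40 = 52.5% | 20/39 = 51.3% | 19/38 = 50.0%, fails |
| 46 | 24/46 = 52.2% | 23/45 = 51.1% | 22/44 = 50.0%, fails |

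Seen from the other side, 18 of 37 users at zero is 48.6% (fails). Adding 3 stoppers at zero gives 21/40 = 52.5% (passes), with 3/40 = 7.5% non-use. Away from the threshold the shift is small: with 75% of 37 users at zero, (27.75 + 3)/40 = 76.9%.

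**Step 4: chance of passing.** Take n = 46 assessed, s stoppers all at zero, and X ~ Binomial(46 − s, p), where p is the true zero-score rate in continuing users. Both s and p are assumptions.

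- As planned: P(X ≥ 24 − s).
- Users only: P(X > (46 − s)/2).
- Stoppers counted as non-zero: P(X ≥ 24).

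| p | s | As planned | Users only | Stoppers non-zero |
|---|---|---|---|---|
| 0.45 | 0 | 20.3% | 20.3% | 20.3% |
| 0.45 | 2 | 30.2% | 20.6% | 13.1% |
| 0.45 | 5 | 49.2% | 25.9% | 5.7% |
| 0.45 | 9 | 76.0% | 27.0% | 1.2% |
| 0.60 | 2 | 93.3% | 88.4% | 81.4% |
| 0.60 | 9 | 99.5% | 89.2% | 33.5% |
| 0.80 | 9 | 100.0% | 100.0% | 99.1% |
| 0.80 | 14 | 100.0% | 100.0% | 82.5% |

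The rise in the users-only column at p = 0.45 mainly reflects odd denominators, where the bare majority is a slightly lower percentage (21/41 = 51.2%).

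**The case against.** Four points can fairly be made for the plan.

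*Use is not hidden.* A reader might infer from SAP 4.3.1 that missed uses are visible only at blinded review. The documents do not support that: they are deviations and should appear in Listing 16.2.2 for all randomised subjects. Subjects are also told to contact the site about reactions, the adverse event listing has a column for action taken on the product, and stinging and burning are asked about at Visit 3. This stands, and it limits the point. What remains is that the Listing 16.2.2 shell holds a text field with no use counts, no summary by arm and no link to the score, and that important violations are left to a separate document.

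*Dropouts are not successes.* A reader might infer that women lost to follow-up inflate the success rate. They have no Day 21 score and Protocol 9.2.5 imputes nothing, so they cannot count as zero. Nor can a woman with no use at all enter the ITT set, since it requires an examination after application, and first use is supervised. The point concerns only women who stop, or largely stop, and still attend.

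*Duration is right for most.* For a compliant completer, last use is the morning of Visit 3, so the derivation agrees with last use. This stands. The figure misstates exposure only for those who stopped earlier.

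*Omitting a per-protocol analysis is a declared choice in a descriptive, non-comparative study of normal use.* This is fair as far as it goes. But the plan still sets a pass mark, and the Protocol defines the target as tolerance after twice-daily application. A summary of use by arm is needed to interpret that result, whichever analysis set is chosen.

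**Conclusion.** The point holds in this form: use data exist, but the planned report neither summarises them by arm nor sets them against the Day 21 result, and a woman who stopped the cleanser and attends Visit 3 at zero counts as a success. The bias runs towards success.

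Its size depends on rates that the documents do not give. In the users-only comparison it could change the verdict only when the zero-score rate is near 50%, where two women are enough at a bare pass. If stoppers are counted as non-zero, the range widens as they become more numerous (60% with 9 of 46 stopping). At 80% or more the verdict is unchanged for up to 9 of 46. All of this assumes that stoppers score zero.

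A reader might go further and conclude that a pass in this study would be unreliable. The documents do not support that: they give no evidence on how many women stopped or on how close either arm is to the threshold. This is a change that should be made, not a defect that invalidates the design.

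**What to change.** 1. Add an ITT table by arm of applications made, missed and extra, and percent of expected. Made and missed come from the CRF totals; SAP 4.3.1 already plans to list additional uses. Before computing percent of expected, reconcile the 42 to 46 in Protocol 5.2 with the first-day and final-morning uses in the same section.
2. Add to Table 14.2.1.1 a sensitivity row giving the Day 21 zero-score proportion among subjects who meet a stated use cut. Where the diary or adverse event record shows that product was stopped for a skin or eye reaction, add a second row counting those subjects as non-zero. Addendum 1 states that its changes were identified after unblinding, so either row specified at that stage must be labelled post hoc.
3. In Listing 16.2.1.1, relabel the current figure as time on study, or derive treatment duration from the last diary-recorded use where that date can be extracted.

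The table and the first row need only CRF totals. The documents do not say that last-use date or reason for stopping the product is in the CRF, so the second row and a new duration may require diary extraction. The other cost is that the sensitivity figure may be less favourable.
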